3. STUDY PROCEDURES

Data Collection

Measures of the primary outcomes (daily weighing and achievement of active minutes goal and red food limit) will be collected daily throughout the study via self-monitoring tools (described below). All study participants will complete objective weight measurements and self-administered online surveys at baseline, 3 months, and 6 months post-intervention. Participants will also complete two dietary recalls at baseline and two dietary recalls at 6 months to measure average dietary intake. Participants will receive \$50, \$25, and \$75 for completing baseline, 3, and 6-month assessments, respectively. Online surveys will include measures of theoretical mediators, other psychosocial constructs, and process measures. We will send emails and texts prompting participants to complete assessments, with follow-up emails and phone calls to non-respondents, as necessary. Measures and timing are described below.

Measures

Primary Proximal Outcome Measures (collected daily)

Intervention messages are intended to promote achievement of 3 daily weight-related behavioral goals: weigh daily, meet a daily active minutes (AM) goal, and stay at or under a daily RF limit. Thus, the primary outcome is the achievement of behavioral goals on the day of randomization (i.e., until 12:00AM).

Met daily weighing goal. Weighing behavior will be objectively measured daily using a smart scale (Fitbit Aria Air, San Francisco, CA) at the participant's home. Participants will be instructed to weigh themselves daily on the scale in light clothing and without shoes. A dichotomous indicator of whether the participant weighed will be calculated.

Met daily active minutes (AM) goal. Participants will have a daily AM goal that may change or stay the same at the beginning of each program week. Fitbit trackers will be used to collect daily AM data, defined by

Fitbit as physical activity of at least moderate-to-vigorous intensity that is accumulated in 10-minute bouts. We will calculate a dichotomous outcome of whether a participant met their daily AM goal (days with no tracker wear are counted as not meeting the goal) on the day of randomization.

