Stayed at or under red foods (RF) limit. Participants will have a daily RF limit that is determined by their sex and baseline weight. Daily RF intake will be calculated from participants' recorded RF in the study app. We will calculate a dichotomous outcome of whether a participant stayed at or under their RF limit (days without complete tracking [defined as tracked RF consumed during dinner plus breakfast or lunch, or if they reached or exceeded their RF limit], are counted as not meeting the RF limit).

Secondary Outcome Measures

Weight will be measured at baseline, 3 months, and 6 months at home using the smart scale. Participants will be asked to weigh themselves three times in a row, upon waking and before eating, in light clothing, without shoes, and the three weights will be averaged and used to calculate absolute weight change and percent weight change over time.

Proportion of days met daily weighing goal will be calculated as the percentage of study days (out of 168) a participant weighed. *Proportion of daily AM goal met* will be calculated as the proportion of daily AM goal met each day of the study using activity tracker data. *Proportion of daily RF limit* will be calculated as the percentage of the daily RF limit recorded each day of the study in the study app. The *total number of AM* and the *total number of RF* on the day of message randomization will be measured for each day of the study. Following the day of message randomization, we will measure *met daily weighing goal tomorrow*, *met daily AM goal tomorrow*, and *stayed at or under daily RF limit tomorrow*.

Tertiary / Exploratory Measures

Behavioral measures

- *Self-reported dietary intake* will be assessed using the NCI's Automated Self-Administered 24-hour Recall (ASA-24; National Cancer Institute) at baseline and 6 months. Participants will complete two unannounced self-reported recalls; one weekday and one weekend day.
- *Self-reported physical activity* at baseline, 3, and 6 months will be assessed with the Paffenbarger Physical Activity Questionnaire (PAQ) which assesses leisure-time activity and provides an estimate of minutes per week of moderate-to-vigorous intensity, and calories/week of light (5 kcal/min), medium (7.5 kcal/min), and high (10 kcal/min) intensity activities (Paffenbarger et al., 1978).

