- *Sedentary Activity* at baseline, 3, and 6 months will be assessed with the Sedentary Behavior Questionnaire from the EARLY trials (Rosenberg et al., 2010; Lytle et al., 2014).

Psychosocial measures

- *Self-efficacy for eating*, measured using the Weight Efficacy Lifestyle Questionnaire (WEL-Q; 20 items).³⁵
- *Self-efficacy for exercise*, measured using the 12-item Self Efficacy and Exercise Habits Survey.³⁶
- *Self-regulation for exercise*, measured with the 10-item Exercise Goal-Setting Scale and the 10-item Exercise Planning and Scheduling Scale.³⁷
- *Motivation for making changes in diet* (15 items) *and exercise* (15 items), measured using the respective Treatment Self-regulation Questionnaires.³⁸
- *Perceived competence for diet* (4 items) *and exercise* (4 items).³⁹
- *Health-related quality of life*, measured using the CDC Healthy Days measure (CDC 1993).
- *Depressive symptoms*, measured using the Center for Epidemiological Studies Depression Scale (CES-D).⁴⁰

- *Weight control strategies*, measured with the Weight Control Strategies Scale (WCSS; 30 items).⁴¹
- *Hunger, restraint, disinhibition* measured using the Three Factor Eating Questionnaire (TFEQ; 51 items).⁴²
- *Perceived stress*, measured using the Perceived Stress Scale (PSS; 10 items).⁴³
- *Binge eating* measured using the revised Questionnaire on Eating and Weight Patterns (QEWP-5).⁴⁴
- *Social comparison orientation* measured using the Iowa-Netherlands Comparison Orientation Measure (INCOM; 11 items).⁴⁵
- *Weight-related information avoidance* (10 items).⁴⁶
- *Relatedness* measured with a scale adapted from Basic Need Satisfaction at Work Scale (3 items).^{47,48}
- *Message relevance* measured using 2 items from our previous work,⁴⁹ which was adapted from previous studies.^{50,51}

Other measures

We will assess several supporting measures, including sociodemographic characteristics, medical events, and medication use. Program engagement (app views, lessons accessed, feedback messages viewed, goals set or modified), process, and adherence measures (self-weighing, activity tracking, red food tracking, daily goal achievement) will be collected throughout the study period and used to calculate behavioral adherence in the prior 7 days and streaks and lapses in goal achievement. Program acceptability and satisfaction will be assessed using post-intervention program evaluation questions and in post-intervention semi-structured interviews after 6 months.

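### The primary red-food outcome scores incompletely tracked days as failures, so a message that only prompts logging can look like a dietary effect, and no planned analysis separates the two

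*Combined protocol and SAP*

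**What the plan says.** All the relevant definitions are in Section 3 (Study Procedures).

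- **Source of the data.** "Daily RF intake will be calculated from participants' recorded RF in the study app". No other daily diet measure exists. The 24-hour recalls are exploratory and taken only at baseline and 6 months.
- **Primary RF outcome.** It is a yes/no indicator of staying at or under the limit. Days without complete tracking "are counted as not meeting the RF limit". Complete tracking is "defined as tracked RF consumed during dinner plus breakfast or lunch, or if they reached or exceeded their RF limit".
- **Primary active-minutes (AM) outcome.** The rule has the same form: "days with no tracker wear are counted as not meeting the goal".
- **Continuous RF secondaries.** The first, a relative measure of intake, "will be calculated as the percentage of the daily RF limit recorded each day of the study in the study app". The second, a plain count of RF, "on the day of message randomization will be measured for each day of the study". Neither has a rule for days with no log or a partial log, and the AM counterparts have none for no-wear days.
- **Next-day RF secondary.** This is binary: "stayed at or under daily RF limit tomorrow". The tracking rule is not restated for it.
- **Tracking itself.** Under Other measures, "adherence measures (self-weighing, activity tracking, red food tracking, daily goal achievement) will be collected throughout the study period". The stated use is to derive prior-week adherence, streaks and lapses.

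Section 4 (Statistical Considerations) provides for a completeness audit and for sensitivity analyses by dropout status. It specifies no analysis by tracking status and no test of message effects on tracking.

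**The concern.** The app that delivers the messages also holds the food log, so a message may well prompt a participant to open the app and log. The plan itself treats self-monitoring as something that varies, since it names streaks and lapses as moderators. Because an unlogged day is a failure by rule, any rise in logging converts some failures into successes even if nobody eats differently. The primary result would then be read as better adherence to the RF limit when part or all of it is better record-keeping.

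This matters for what the trial is for. Section 1 (Study Objectives) says that messages found efficacious will go into an optimized intervention for a later randomized trial of weight loss. Messages chosen because they improve recording could be carried forward as dietary interventions. The open coding of the continuous secondaries adds a second risk. Depending on a choice not yet stated, they could agree with the primary, disagree with it, or show nothing.

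**Working it through.** **The plan's own figures.** Usable days: 168 × .83 + 84 × .17 = 153.72, about 154. Person-days: 201 × 154 = 30,954, as stated. The detectable range of .04 to .13 cannot be reproduced, because message availability is named as an input but given no value. With a two-sided 5% test, 80% power and randomization probability 0.5, d = 2.80 / √(201 × 154 × availability × 0.25). This gives .032 at availability 1, .040 at 0.63 and .130 at 0.06. The range is attainable, and I take it as stated.

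**Logging-only effect on the primary.** The inputs below are assumptions; the documents give none of them. Let L be the probability that a day is completely tracked and q the probability that a tracked day is within limit. Eating, and so q, is unchanged by the message.

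P(met) = L × q; shift = ΔL × q; d = shift / √(p(1 − p)), with p = L × q before the change.

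| Tracking | q | Shift in P(met) | d |
|---|---|---|---|
| 60% to 62% | .60 | .02 × .60 = .012 | .012 / √(.36 × .64) = .025 |
| 60% to 65% | .60 | .05 × .60 = .030 | .030 / √(.36 × .64) = .0625 |
| 50% to 60% | .60 | .10 × .60 = .060 | .060 / √(.30 × .70) = .131 |

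Over a wider grid (L from 40% to 80%, q from 40% to 80%), with d now scaled by the pooled SD of the two conditions, a 5-point logging effect gives d of about .04 to .085. A 2-point effect gives about .02 to .03.

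**The same effect on the continuous RF secondaries.** Assume that logged days average 90% of the limit with SD 50%, and that tracking goes from 60% to 65%.

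- If untracked days enter as zero, the mean goes from .60 × 90 = 54.0% to .65 × 90 = 58.5% of the limit. That is +4.5 points, an apparent worsening. The variance at tracking L is L(.50² + .90²) − (.90L)², which is .344 at .60 and .347 at .65. The SD is about .588 and d = .045 / .588 = .077.
- If untracked days are missing, the expected shift is 0, but only because this model makes logging unrelated to intake. Otherwise the bias could go either way.

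**Active minutes.** A no-wear day is a failure on the primary. If it entered as zero, it would also be the worst value on the continuous measures. More wear would therefore push both in the favourable direction.

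**What scoring untracked days as met would show.** P(met) becomes 1 − L(1 − q).

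- Logging only (L .60 to .65, q = .60): 1 − .60 × .40 = .760 falls to 1 − .65 × .40 = .740. The two scorings give +3 and −2 points around a true dietary effect of zero.
- Logging and eating both improve (L .60 to .65, q .60 to .63): the primary goes from .360 to .65 × .63 = .4095. Scored as met, .760 becomes 1 − .65 × .37 = .7595. A real improvement disappears, so this scoring works as a bound and not as a test that a dietary claim must pass.

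**The case against.** **The composite is declared.** The plan states openly that incomplete days fail, makes daily self-monitoring part of the core intervention, and frames the outcome as adherence. Counting non-tracking as non-adherence is a legitimate choice. This stands: the scoring is not an error. What it does not supply is a basis for reading a positive result as a change in eating.

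**The data to separate the two are collected.** This also stands. The gap is a missing analysis, not a missing measurement.

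**The size is assumed.** Correct. A 2-point logging effect gives about .025, below the whole stated detectable range, and reaching .13 took an assumed 10-point effect. The gain is also not universal. Logging an over-limit day leaves a failure a failure, and adding a meal to a day already complete can turn a success into a failure.

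**A stronger reading is tempting.** A reader might infer that untracked days count as zero red foods in the secondary outcomes, so that these must contradict the primary. The documents do not support that. They state neither zero nor missing, and zero is only one reading of a measure taken each day from app records. The point also reaches only the two continuous RF measures. The next-day RF outcome is binary, and if the primary rule carries over, it would count untracked days as failures too. Nor does the opposite movement extend to active minutes.

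**Conclusion.** The concern holds in a limited form. By its stated rule, the primary RF outcome measures 'tracked and within limit', and a logging effect alone can raise it. With tracking moving from 60% to 65% and 60% of tracked days within limit, both assumed, the artefact is +3 points, d about .06, inside the planned range of .04 to .13. At 2 points of logging it is about .025 and would matter little. No specified analysis would show which case applies.

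For the two continuous RF secondaries, the demonstrable defect is the absence of a rule for untracked days. Movement opposite to the primary is conditional on zero coding. The AM primary shares the structure through no-wear days, but there the continuous measures would move the same way. It would go too far to say that the trial cannot distinguish recording from eating: it collects what is needed to examine message effects on tracking and has not planned to use it that way. This should be settled before the data are analysed.

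**What to change.** 1. **Companion outcomes.** Run every Aim 1 contrast in the same GEE on RF tracking and on tracker worn. Define RF tracking as dinner plus breakfast or lunch logged, without the clause that makes a day complete once the limit is reached, because that clause depends on intake. Say how a meal with no red foods is recorded, so that the meal rule does not depend on intake either. State whether these contrasts fall inside the multiplicity correction.
2. **Interpretation.** Describe the RF primary as 'tracked and within limit'. Read a positive result as dietary only in light of the tracking result. Show untracked-as-met as a bounding sensitivity analysis, not as a required condition.
3. **Continuous RF and AM secondaries.** Do not enter days with no log or no wear as zero. Treat them as missing under a completeness rule that does not depend on the amount recorded, with bounds or weighting. The primary's own completeness rule is unsuitable here: it would keep partly logged high-intake days and drop partly logged low-intake ones.

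The cost is a few extra model runs on data already collected. The limitation is that results on tracked or worn days rest on selection after randomization, which is why the bounds or weights are needed.

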4. STATISTICAL CONSIDERATIONS

Sample Size and Power

Our power analysis is based on a sample size calculator built in an R package (MRT-SS)⁵² for detecting proximal treatment effects in microrandomized trials developed by Liao et al,⁵³ expanding on more general results for sample size calculations for longitudinal trials from Tu et al.⁵⁴ Inputs to the sample size calculator are: desired alpha (.05), the number of outcome occasions ($T=168$ days for each proximal outcome), average probability of message availability each day, the randomization probability for a given message if it is available (0.5), and the standardized proximal treatment effect $\bar{d}_t = \sum_t d_t / T$ across all time points. Based on our prior research¹⁶ and the previous MRTs with published effects sizes,^{31,32,55} we assume that \bar{d}_t ranges from .03 to .15. Based on our previous studies with young adults^{56,57} and the pilot MRT,¹⁶ assuming 17% attrition by day 168, we estimated that a sample size of $N=201$ would be required to have an average of 150 usable days per person ($168 \text{ days} \times .83 + 84 \text{ days} \times .17 = 154$), for a total of 30,954 person-day observations ($N=201 \times 154$; i.e., over 4400 person-day observations per each of 7 BCT message interventions across 3 behaviors). This is consistent with a prior MRT that evaluated 6061 available decision points to test 2 different options for an intervention component (i.e., walking suggestions, anti-sedentary suggestions) among 37 participants.³² We will use all available data points in these analyses and test the sensitivity of our findings to dropout status by conducting completer-only and dropper-only analyses. The estimated minimum detectable standardized effect size with 80% power across the planned analyses ranges from .04 to .13.

Statistical Analysis Plan

Data analysis will be performed using R statistical software (version 4.0.3). Baseline demographic and descriptive characteristics will be summarized globally, using frequencies and percentages for categorical variables, and means and standard deviations (SD) for inherently quantitative variables. Prior to conducting data analyses, we will audit the data for completeness and quality, including missing data. We will evaluate response distributions to ensure that they meet assumptions of planned analyses (see below), including the detection of outliers.

Analysis of primary outcomes

We will test: 1) whether any intervention message (versus no message) increases adherence to daily weight loss behaviors among young adults, 2) whether a behavior-specific message (versus not receiving the behavior-specific message) increases adherence to the respective behavioral goal, and 3) finally the unique effect of each BCT message for the three proximal outcomes. We will use generalized estimating equations (GEE) with an independence working residual correlation matrix to account for nesting of observations within individuals.⁵⁸ and use Benjamini-Hochberg-Storey correction for multiple testing.⁵⁹

Analysis of whether effects of BCT messages change over time

We will also examine whether the effects of BCT messages on daily adherence to weight loss behaviors change over time (week in program, time of day) and, if so, the nature of the change (e.g., when effects disappear). Thus, we will expand upon the model described above by: 1) including linear and quadratic main effects of time and interaction terms, between an indicator of day in the program and treatment assignment, to test whether the treatment effect changes over time.⁵⁸ We will examine differences in the average and estimated time trends in treatment effects of receiving a behavior-specific message, and then the unique effect of each BCT message for the three proximal outcomes.

Analysis of whether effects of BCT messages are moderated by participants' contextual factors

We will evaluate whether the causal effect of receiving a BCT message interacts with participants' contextual factors, including past behaviors and individual characteristics. We will use standard moderation analysis within the GEE framework for these analyses, which involves the inclusion of main effects and interaction terms. Significant moderation effects will be probed using simple slopes analysis to determine the conditional region and direction of significance. The primary moderators to be tested are participants' 7-day history of contextual factors at the time of randomization (achievement of weight-related behavioral goals, streaks and lapses in self-monitoring, weight change, previous BCT messages received). Exploratory time-invariant potential moderators include demographic and health characteristics (e.g., sex, age, baseline BMI).

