- Evaluate the effects of each behavior change technique message (i.e., BCT message) on daily adherence to weight loss behaviors in a 6-month micro-randomized trial among young adults.
- Determine whether the effects of BCT messages on proximal outcomes change over time.
- Assess whether the effects of BCT messages on proximal outcomes are moderated by participants’ contextual factors.

Test Article(s)
(If Applicable)

All participants will receive a core 6-month weight loss intervention that includes evidence-based lessons, behavioral skills training, and daily self-monitoring of weight, dietary intake, and physical activity.

Study Design

The Nudge trial applies the Multiphase Optimization Strategy (MOST) framework and uses a microrandomized trial design to test the effects of 7 types of behavior change technique (BCT) messages on achievement of daily weight-related goals among 201 young adults. All participants will receive a 6-month behavioral weight loss intervention using our Nudge mobile app, which includes evidence-based weekly lessons, tailored feedback, self-monitoring, and daily BCT messages. Participants will receive a wireless scale, activity tracker, and track “red” foods (high-calorie foods) in the app and have 3 goals: weigh daily, a daily active minutes goal that gradually increases if met, and a daily red foods limit. At 3 decision points per day, participants will be microrandomized to receive or not receive 1 of 7 types of BCT messages. The outcome to be tested is the effect of BCT messages on achievement of same-day goal achievement (weighing, active minutes goal, red food limit). Assessments of the primary outcomes will occur daily, with assessments of secondary outcomes at 0, 3 and 6 months.

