2.2 Intervention Overview

All participants will receive a 6-month core intervention adapted from the Diabetes Prevention Program specially for young adults and to be delivered remotely via an automated program. The program, Nudge, will be delivered through a native smartphone app that includes weekly lessons, weekly tailored feedback, a native food log to track red foods, visual displays of behavioral progress, and in-app messages. All participants will receive a wireless scale and an activity tracker (Fitbit, San Francisco, CA) in the mail followed by an individual videochat session with an interventionist. For each of the 24 weeks of the program, at 3 scheduled time points per day, participants will be randomized to receive or not receive a BCT message promoting achievement of proximal weight management behaviors (weighing, activity, red food intake). Thus, participants will receive 0-3 messages per day. The primary outcome is same-day achievement of daily goals (weighing, active minutes goal, red food limit), evaluated among observations in which participants received a message compared to observations in which the participant did not receive a message.

Questions answered through Nudge MRT	

 Does providing a BCT message increase goal attainment on the same day it is delivered? (Aim 1) Do each of the BCT message types have different effects on goal attainment? (Aim 1) Do BCT messages' effects change over time? If so, what is the nature of the change (i.e., when does the effect disappear)? (Aim 2) Do BCT messages work differently when delivered under different contexts (e.g., time in program, time of day, previous dose of BCT messages, recent behaviors)? (Aim 3) 	
Intervention components to be tested across 3 behaviors: 7 behavior change techniques (BCT messages)	
1.4 Action planning	Message prompts detailed planning of performance of behavior via implementation intentions
1.6 Discrepancy between current behavior and goal	Message draws attention to discrepancies between a person's current behavior and previously set outcomes goals, behavioral goals, or action plans
2.7 Feedback on outcome of behavior	Message provides feedback on the outcome of performance of the behavior (i.e., weight)
3.1 Social support	Message advises on or provides social support for performance of the behavior
6.2 Social comparison	Message draws attention to others' performance to allow comparison with person's own performance

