10.4 Social reward	Message delivers positive reinforcement, if and only if there has been effort and/or progress in performing behavior
15.3 Focus on past success	Message advises to think about or list previous successes in performing the behavior (or parts of it)

Study Population

Individuals will be eligible if they meet the following criteria: age 18-39; body mass index (BMI) of 25-45 kg/m²; English-speaking and writing; and own a smartphone with a data and texting plan. Exclusion criteria include being currently pregnant, pregnant within the past 6 months, or planning to become pregnant within the next 6 months; type 1 diabetes or receiving medical treatment for type 2 diabetes; a heart condition, chest pain, or other health problems that influence the ability to follow physical activity recommendations; lost 10 pounds or more in the past 6 months; history of weight loss surgery or planned weight loss surgery in the next year; currently taking weight loss medications; report a past diagnosis of or receiving treatment for an eating disorder; current symptoms of alcohol or substance dependence; untreated thyroid disease or any changes (types or dose) in thyroid medication in last 6 months; hospitalization for depression or another psychiatric disorder in the past 12 months or history of bipolar or other psychotic disorder; another member of the household is a participant or staff member on this trial; currently participating in another weight loss, nutrition, or physical activity study or program; reason to suspect the participant would not adhere to the study intervention; reside outside of the United States; have participated in another study conducted by the UNC Weight Research Program within the past 12 months. Individuals that reported joint problems, some prescription medications, or current treatment for hypertension or hyperlipidemia will be required to obtain written physician consent to participate.

The trial is registered on clinicaltrials.gov (NCT05625061) and was approved by the Institutional Review Board at the University of North Carolina at Chapel Hill on May 13, 2022.

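### The .5 message probability cannot be every eligible BCT type's own chance, and the BCT-specific contrasts name no eligibility restriction, assignment probabilities or matched comparator, so they can be biased in either direction.

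*Combined protocol and SAP*

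**What the plan says.** - **Randomization.** The Synopsis (Study Design) states: "At 3 decision points per day, participants will be microrandomized to receive or not receive 1 of 7 types of BCT messages". Section 2.2 gives a range of zero to three messages a day, so at most one message is sent per decision point.
- **Power.** Section 4, Sample Size and Power, lists "the randomization probability for a given message if it is available (0.5" among the calculator inputs. It also names "average probability of message availability each day" but gives no value for it.
- **Eligibility.** Section 2.1 says messages are tailored to recent behavior and context. In the table in section 2.2, social reward is delivered "if and only if there has been effort and/or progress in performing behavior". Action planning is described only as "Message prompts detailed planning of performance of behavior via implementation intentions", with no condition. Social support and social comparison also carry none.
- **BCT-level analysis.** Aim 1 (Study Objectives) sets each of the seven types against no message. Section 4, Analysis of primary outcomes, plans to test "finally the unique effect of each BCT message for the three proximal outcomes" by GEE with an independence working correlation and a multiplicity correction.
- **Not stated.** The documents do not say how a type is chosen when several qualify, what each type's probability is, or which no-message points serve as its comparator. The primary analysis names no weights and no restriction to eligible points.

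**The concern.** A micro-randomized contrast is protected by randomization only if the probability of the treatment is constant over the points compared, or is known and used. For any message against none, a constant .5 is enough. For one type against none it is not. If a type's chance depends on which other types qualify, or on whether it qualifies at all, the points that received it come from a different mix of contexts than the no-message points. Where those contexts differ in goal achievement, the difference appears as a message effect.

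That is plausible here. Recent goal achievement, streaks and lapses are the plan's own primary moderators of the message effect, and recent goal achievement is a natural predictor of today's.

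Aim 1 includes the type-specific effects, and the messages found efficacious are to form the optimized JITAI for a later RCT. A spurious difference of a few points could keep or discard a message type.

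**Working it through.** **1. The plan's own figures.** From Sample Size and Power: 168 × .83 + 84 × .17 = 153.7, stated as 154. Then 201 × 154 = 30,954 person-days, and 30,954 / 7 = 4,422, stated as over 4400. These reproduce.

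The minimum detectable range of .04 to .13 cannot be reproduced, because availability is not given. Taking "desired alpha (.05" as two-sided, 80% power and a normal approximation:

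MDE = (1.960 + 0.842) / √(30,954 × availability × .5 × .5)

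- At availability 1 this gives .032.
- .04 needs availability (2.802/.04)² / 7,738.5 ≈ .63.
- .13 needs availability (2.802/.13)² / 7,738.5 ≈ .06.

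The range is attainable, but it cannot be verified.

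**2. Can .5 be each type's own chance?** With k types eligible and at most one sent, the chances sum to .5k: 1.0 at k = 2 (no room for no message), 1.5 at k = 3 and 3.5 at k = 7. So it cannot hold for every eligible type once two or more qualify. If .5 is the chance of any message and is shared equally, each type's chance is .5/k: .25, .167, .125 and .071 for k = 2, 3, 4 and 7.

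**3. Bias for an always-eligible type.** All values here are assumptions. The true effect is zero, half the points are in a good context with goal rate 60% and half in a poor context with 40%, and the chance of any message is .5, shared equally. The pooled no-message rate is 50%. Points that received the type weight each context by 1/k.

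- k = 4 good, 3 poor: share of good = (1/4) / (1/4 + 1/3) = .4286. Rate = 40% + 20% × .4286 = 48.6%. Bias -1.4 points.
- k = 3 good, 4 poor: share .5714, rate 51.4%. Bias +1.4 points.
- Equal k, or equal goal rates: bias 0.

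**4. Bias for a conditional type.** Suppose a type is eligible only in the 60% context. Its rate is 60% against a pooled 50%, a bias of +10 points. Restricted to eligible points it is 60% against 60%, a bias of 0. Weighting alone cannot repair this, because the type's probability is zero in the other context.

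**5. Simulation.** 201 × 154 occasions, 200 runs, cluster-robust standard errors, zero true effect, always-eligible type, assumed goal rates 55% and 45%, tested at .05:

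| Eligible types (good / poor) | Expected unweighted bias | Rejection, unweighted | Rejection, weighted | Rejection, same candidate withheld |
|---|---|---|---|---|
| 2 / 6 | +2.5 points | 88% | 4.5% | 6.5% |
| 3 / 5 | +1.25 points | 35% | 4.5% | 5.5% |

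With a fixed draw chance of .25 in both contexts, the unweighted contrast showed -0.1 points and 5% rejection. The bias therefore comes from the varying chance, and both remedies remove it within simulation error.

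**The case against.** The strongest reply is that the .5 is only a calculator input, and that it fits a valid design: draw one candidate type, then send or withhold it at .5. Compared with its own withheld occasions, every type then has a constant .5 chance and needs no weights. The plan divides its person-days by seven, which suits that reading. The primary analysis also cites a methods paper on time-varying causal effects, which may prescribe weighting, although its content is not in the documents.

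Much of this stands. A reader might infer that type-level chances must vary with the number of eligible types and that the contrasts are biased in a known direction. The documents do not support that. They give no count of eligible types, no selection rule and no goal rates by context. The table rows describe techniques and may not be the full eligibility rules.

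A reader might also infer that the type-level minimum detectable effect is pushed above the assumed maximum of .15. That does not follow either. On the approximation above, .13 already implies about 6% availability per type, so scaling it up further for many types eligible together would be inconsistent. Even with all seven types eligible on every person-day and .5 shared among them, the figure is 2.802 × √(1/(30,954 × .5/7) + 1/(30,954 × .5)) = .064.

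The reply does not settle the analysis. Aim 1 names no message as the comparator, not the same candidate withheld. Against pooled no-message points, a drawn candidate's chance is .5 times its draw chance in that context, which can still vary. A priority rule makes the draw chance 0 or 1 by context. A fixed draw chance protects an always-eligible type, but not one such as social reward.

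**Conclusion.** The point holds in a limited form. It is certain that .5 cannot be every eligible type's own chance when two or more qualify. It is also clear that the plan leaves undefined the type-level probabilities, the eligible points and the comparator on which the BCT-specific contrasts depend. Taken literally, with each type against pooled no-message points, those contrasts can be biased in either direction.

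Bias requires three things together: a type chance that varies with context, a context that predicts goal achievement, and an analysis pooled over contexts without restriction, weights or a matched comparator. The documents make each plausible and fully confirm none. The -1.4, +1.4 and +10 points and the rejection rates illustrate the mechanism under assumed values; they do not estimate this trial's bias.

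The any-message contrast, listed first among the primary tests, is unaffected if .5 is constant.

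**What to change.** 1. **Sample Size and Power.** State whether .5 is the chance of any message or the chance of sending a drawn candidate. Give the type-level chance and the availability behind the BCT-level minimum detectable effect, so that the figure can be checked.
2. **Analysis of primary outcomes.** Restrict each BCT contrast to decision points where that type was eligible, using the logged eligible set and assignment probabilities. Within those points, either compare sent with withheld for the same drawn candidate, or weight rows by the inverse of the known assignment probability. The restriction is needed with either choice, because weighting without it leaves conditional types such as social reward biased.

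The cost is analysis-plan wording, a dependable log of eligible types and probabilities at each decision point, some extra analysis work and a small loss of precision. The randomization itself does not change.
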